#### **5.4.3 Trial Blinding/Masking**

This is an open-label trial; therefore, the Sponsor, investigator and subject will know the treatment administered.

#### **5.5 Treatment Allocation**

#### **5.6 There will be no randomization utilized in this study. Aside from the predetermined dose-escalation (and individual dose modifications, if needed, all subjects will receive the same treatment). Concomitant Medications/Vaccinations (allowed & prohibited)**

Medications or vaccinations accepted or prohibited to use in this trial are detailed in following paragraphs. If there is a clinical indication for one of these medications or vaccinations prohibited during the trial, discontinuation from trial therapy may be required. The investigator should discuss any questions regarding this with the Merck Clinical team. The final decision on any supportive therapy or vaccination rests with the investigator and/or the subject's primary physician.

##### **5.6.1 Acceptable Concomitant Medications**

All treatments that the investigator considers necessary for a subject's welfare may be administered at the discretion of the investigator in keeping with the community standards of medical care. All concomitant medication will be recorded on the electronic Case Report Form (eCRF) in OnCore including all prescription, over-the-counter (OTC), herbal supplements, and IV medications and fluids. If changes occur during the trial period, documentation of drug dosage, frequency, route, and date may also be included on the eCRF.

All concomitant medications received within 28 days before the first dose of trial treatment and 30 days after the last dose of trial treatment should be recorded. Concomitant medications administered after 30 days after the last dose of trial treatment should be recorded for SAEs and ECIs as defined in Section 7.3.

##### **5.6.2 Prohibited Concomitant Medications**

Subjects are prohibited from receiving the following therapies during the Screening and Treatment Phase (including retreatment for post-complete response relapse) of this trial:

- Antineoplastic systemic chemotherapy or biological therapy
- Immunotherapy not specified in this protocol
- Chemotherapy not specified in this protocol
- Investigational agents other than pembrolizumab and Poly-ICLC
- Radiation therapy
  - Note: Radiation therapy to a symptomatic solitary lesion or to the brain may be allowed at the investigator's discretion.
- Live vaccines within 30 days prior to the first dose of trial treatment and while participating in the trial. Examples of live vaccines include, but are not limited to, the following: measles, mumps, rubella, varicella/zoster, yellow fever, BCG, and typhoid vaccine.
- Systemic glucocorticoids for any purpose other than to modulate symptoms from an event of clinical interest of suspected immunologic etiology. The use of physiologic doses of corticosteroids may be approved after consultation with the Sponsor.

Subjects who, in the assessment by the investigator, require the use of any of the aforementioned treatments for clinical management should be removed from the trial. Subjects may receive other medications that the investigator deems to be medically necessary.

The Exclusion Criteria describes other medications which are prohibited in this trial. There are no prohibited therapies during the Post-Treatment Follow-up Phase.

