### 4.2 Target lesions

#### 4.2.1 Documentation of target lesions

A maximum of 5 measurable lesions, with a maximum of 2 lesions per organ (including lymph nodes), representative of all lesions involved should be identified as TL at baseline. Target lesions should be selected on the basis of their size (longest diameter for non-nodal lesions or short axis for nodal lesions), but in addition should be those that lend themselves to reproducible repeated measurements. It may be the case that, on occasion, the largest lesion does not lend itself to reproducible measurement in which circumstance the next largest lesion, which can be measured reproducibly, should be selected.

The site and location of each TL should be documented as well as the longest diameter for non-nodal lesions (or short axis for lymph nodes). All measurements should be recorded in millimeters. At baseline the sum of the diameters for all TL will be calculated and reported as the baseline sum of diameters. At follow-up visits the sum of diameters for all TL will be calculated and reported as the follow-up sum of diameters.

Special cases:

- For TL measurable in 2 or 3 dimensions, always report the longest diameter. For pathological lymph nodes measurable in 2 or 3 dimensions, always report the short axis.
- If the CT/MRI slice thickness used is  $>5$  mm, the minimum size of measurable disease at baseline should be twice the slice thickness of the baseline scan.
- If a lesion has completely disappeared, the longest diameter should be recorded as 0 mm.

- If a TL splits into two or more parts, then record the sum of the diameters of those parts.
- If two or more TLs merge then the sum of the diameters of the combined lesion should be recorded for one of the lesions and 0 mm recorded for the other lesion(s).
- If a TL is believed to be present and is faintly seen but too small to measure, a default value of 5 mm should be assigned. If an accurate measure can be given, this should be recorded, even if it is below 5 mm.
- If a TL cannot be measured accurately due to it being too large, provide an estimate of the size of the lesion. Although a visit response of PD will be assigned in the vast majority of these cases, a case should be flagged and reviewed by the Study Physician in a blinded fashion if use of the estimated size in the calculation of TL would not give an overall visit response of PD.

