- When a TL has had any intervention eg, radiotherapy, embolization, surgery, during the study, the size of the TL should still be provided where possible.

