#### 4.2.2 Evaluation of target lesions

This section provides the definitions of the criteria used to determine objective tumor visit response for TL (see [Table 2](#)).

Table 2	Evaluation of target lesions
Complete Response (CR) lymph	Disappearance of all TLs since baseline. Any pathological nodes selected as TLs must have a reduction in short axis to <10 mm.
Partial Response (PR) taking	At least a 30% decrease in the sum of the diameters of TLs, as reference the baseline sum of diameters.
Stable Disease (SD)	Neither sufficient shrinkage to qualify for PR nor sufficient increase to qualify for PD.
Progression of disease (PD)	At least a 20% increase in the sum of diameters of TLs and an absolute increase of at least 5 mm, taking as reference the smallest sum on study (this includes the baseline sum if that is the smallest on study).
Not Evaluable (NE) evaluable	Only relevant if any of the TLs were not assessed or not or had a lesion intervention at this visit. Note: if the sum of diameters meets the progressive disease criteria, progressive disease overrides not evaluable as a TL response.

---

CR Complete response; PR Partial response; PD Progression of disease; NE Not evaluable; SD Stable disease; TL Target lesion.

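### The appendix makes a locally treated target lesion not evaluable only at the visit of the intervention, so later shrinkage from permitted radiotherapy could count in the primary ORR

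*Combined protocol and SAP*

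**What the plan says.** - **Permitted radiation.** Section 5.6.2 lists radiation among the prohibited treatments, with a note: "Radiation therapy to a symptomatic solitary lesion or to the brain may be allowed", if the investigator so decides. The note does not say whether the irradiated lesion may be a target lesion. The section closes by saying that subjects who "require the use of any of the aforementioned treatments for clinical management should be removed from the trial".
- **Measurement of a treated lesion.** Appendix 11.4, section 4.2.1: "When a TL has had any intervention eg, radiotherapy, embolization, surgery, during the study, the size of the TL should still be provided where possible". The same list has a general convention for vanished lesions: "If a lesion has completely disappeared, the longest diameter should be recorded as 0 mm".
- **Scoring of a treated lesion.** In Appendix 11.4, section 4.2.2, Table 2, NE applies when a target lesion was not assessed, was not evaluable, "or had a lesion intervention at this visit". The one stated exception is that "progressive disease overrides not evaluable as a TL response".
- **Overall response and confirmation.** Table 4 of the appendix turns a target-lesion NE into an overall NE unless there is non-target progression or a new lesion. A CR or PR is to be confirmed at the next scheduled scan, at least 4 weeks later.
- **Endpoint.** Section 8.3 makes the RECIST 1.1 response rate primary for Phase II. Section 8.5.1 defines ORR as CR plus PR over all participants in the dataset. Section 1 gives the control as historical.

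**The concern.** The NE row exists so that the effect of local treatment is not read as an effect of the study drugs. Its wording ties it to a single visit. Table 2 is applied scan by scan, and scans are about 9 weeks apart. Nothing says what happens at the scan after that one, when the lesion is measurable again and its recorded size reflects the radiotherapy.

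The appendix already treats earlier irradiation as a lasting problem: under its section 2, a lesion irradiated before entry is not measurable unless it has since progressed. No matching lasting rule covers irradiation during the study.

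At stake is the primary estimate. With one arm and a historical comparator, a response produced by radiation is credited to the combination, and no control group receives the same credit.

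**Working it through.** The check has two parts: follow the scoring rules through successive scans, then size the effect of one miscounted responder.

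**Scoring rules in order**

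1. Phase 2 patients must have measurable disease (Section 5.2, criterion 3), so each has at least one target lesion. If the irradiated lesion is the patient's only lesion, it is the target lesion.
2. At the visit with the intervention, Table 2 gives NE and Table 4 gives overall NE, absent non-target progression or new lesions. That visit contributes no response.
3. At the next scan, about 9 weeks later, there was no intervention at that visit. The lesion is assessed and its size recorded, so on a literal reading NE no longer applies. The sum of diameters is compared with baseline, and a fall of at least 30% is a PR. Table 4 makes it an overall PR if there is no non-target progression or new lesion.
4. The following scheduled scan confirms it if the shrinkage persists.
5. Section 8.5.1 counts any CR or PR and has no cut-off at local treatment.

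**How much the treated lesion must shrink.** Let *w* be its share of the baseline sum and *s* its fractional shrinkage, with the other target lesions unchanged. The sum falls by *w* × *s*, and a PR needs *w* × *s* ≥ 0.30. For equal-sized lesions:

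| Target lesions | *w* | Shrinkage needed, 0.30/*w* |
|---|---|---|
| 1 | 1 | 0.30 |
| 2 | 0.50 | 0.60 |
| 3 | 1/3 | 0.90 |
| 4 | 0.25 | 1.20 (impossible) |
| 5 (the maximum) | 0.20 | 1.50 (impossible) |

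So, if the other lesions do not change, the treated lesion must carry at least 30% of the baseline sum.

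**The plan's own figure.** Section 8.4 gives 27 patients for 5% against 20%, 80% power and alpha 0.05. It states neither sidedness nor a cut-off. With an assumed exact one-sided rule of at least 4 responders:

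- P(X ≥ 4 | 27, 0.05) = 0.0437
- P(X ≥ 4 | 27, 0.20) = 0.8177
- with 26 patients the power is 0.7932

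The 27 is therefore reproduced and is not in dispute.

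**Effect of a miscounted responder on the estimate** (exact 95% CI)

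- 3/27 = 11.1% (2.4% to 29.2%)
- 4/27 = 14.8% (4.2% to 33.7%)

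**Effect on the chance of reaching 4/27 at a true 5% rate.** If *k* patients are certain to be miscounted, the other 27 − *k* must supply 4 − *k* responses:

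- *k* = 0: 0.044
- *k* = 1: P(X ≥ 3 | 26, 0.05) = 0.139
- *k* = 2: P(X ≥ 2 | 25, 0.05) = 0.358

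If local treatment instead adds a few points to the rate (assumed range):

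| Added points | Expected extra responders | P(X ≥ 4 of 27) |
|---|---|---|
| 0 | 0 | 0.0437 |
| 1 | 27 × 0.01 = 0.27 | 0.0755 |
| 2 | 27 × 0.02 = 0.54 | 0.1166 |
| 3 | 27 × 0.03 = 0.81 | 0.1658 |

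**The case against.** The strongest reply is that the appendix already handles this. NE applies to a lesion with an intervention, only progression overrides it, and NE is not a response. Recording the size then has an obvious purpose: it lets progression be detected. Radiotherapy is also seldom given on the day of a scan, so a strictly literal reading would leave the clause almost without use, and a sensible assessor might carry NE forward. That reading is reasonable, but the text does not require it, and two assessors could differ. This is what remains of the concern.

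Several stronger readings are tempting, and the documents do not support them:

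- **That local treatment simply counts as a response.** It does not at the visit of the intervention. Only later visits are open, and only if the shrinkage is large enough, no other progression occurs and a later scan confirms it.
- **That any permitted radiation is affected.** The appendix lists brain metastases as non-measurable, so they cannot be target lesions.
- **That embolization or resection is permitted.** Both appear only as examples in the measurement rule. The exception in 5.6.2 covers radiation. The 0 mm convention is general and does not mention treated lesions.
- **That 5.6.2 plainly contradicts itself.** The note reads more naturally as a specific exception to the ban. The glucocorticoid item has the same structure, and Table 3 and Section 5.7.1 rely on that item's exception. Different handling between sites is possible but not shown.
- **That the probabilities above estimate the bias.** They measure the assumed frequency and cut-off, not anything the documents report.

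**Conclusion.** The gap is real but narrow. The existing NE rule is not stated to continue after the visit of the intervention, and nothing else in Appendix 11.4 or Section 8 closes that route into the primary ORR. Affected patients are probably few: the irradiated lesion must be a target lesion outside the brain and, with the others unchanged, must make up at least 30% of the baseline sum. The documents give no rate of on-study radiotherapy, so the size of any bias cannot be estimated.

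One case would matter in a trial of 27, moving the estimate by 1/27 = 3.7 percentage points. The success probabilities also rest on a four-responder cut-off that the plan does not state; Section 8.5.1 commits only to an estimate with an exact interval. This is a cheap clarification worth making. It does not show that the planned analysis is biased.

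**What to change.** 1. In Appendix 11.4, Table 2, NE row, take the clause "or had a lesion intervention at this visit" and insert *or any earlier on-study* before its last word. Keep the override for progression. A response first met after local treatment of a target lesion then does not count as CR or PR for ORR.
2. State how a response first met before the intervention but not yet confirmed is handled, because its confirmatory scan would now be NE.
3. Put the same rule in Appendix 11.3, whose irRC definitions have no provision for local treatment. Section 8.3 makes that assessment exploratory.
4. Optionally, reconcile the wording of the 5.6.2 note with the section's closing sentence so that sites read them alike. Which clinical rule applies is for the sponsor and investigators to decide.

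The cost is one phrase in a table row and a sentence or two elsewhere. The downside is that a genuine systemic response first seen after local treatment of a target lesion would be lost, so the ORR could be slightly lower. Progression in these patients can still be scored through lesion size, non-target lesions and new lesions.

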## 5.7 Rescue Medications & Supportive Care

### 5.7.1 Supportive Care Guidelines

Subjects should receive appropriate supportive care measures as deemed necessary by the treating investigator. Suggested supportive care measures for the management of adverse events with potential immunologic etiology are outlined below. Where appropriate, these guidelines include the use of oral or intravenous treatment with corticosteroids as well as additional anti-inflammatory agents if symptoms do not improve with administration of corticosteroids. Note that several courses of steroid tapering may be necessary as symptoms may worsen when the steroid dose is decreased. For each disorder, attempts should be made to rule out other causes such as metastatic disease or bacterial or viral infection, which might require additional supportive care. The treatment guidelines are intended to be applied when the investigator determines the events to be related to pembrolizumab.

Note: if after the evaluation the event is determined not to be related, the investigator does not need to follow the treatment guidance (as outlined below). Refer to the dose modification section.

It may be necessary to perform conditional procedures such as bronchoscopy, endoscopy, or skin photography as part of evaluation of the event.

- **Pneumonitis:**

- For **Grade 2 events**, treat with systemic corticosteroids. When symptoms improve to Grade 1 or less, steroid taper should be started and continued over no less than 4 weeks.
- For **Grade 3-4 events**, immediately treat with intravenous steroids. Administer additional anti-inflammatory measures, as needed.
- Add prophylactic antibiotics for opportunistic infections in the case of prolonged steroid administration.

- **Diarrhea/Colitis:**

Subjects should be carefully monitored for signs and symptoms of enterocolitis (such as diarrhea, abdominal pain, blood or mucus in stool, with or without fever) and of bowel perforation (such as peritoneal signs and ileus).

- All subjects who experience diarrhea/colitis should be advised to drink liberal quantities of clear fluids. If sufficient oral fluid intake is not feasible, fluid and electrolytes should be substituted via IV infusion. For Grade 2 or higher diarrhea, consider GI consultation and endoscopy to confirm or rule out colitis.
- For **Grade 2 diarrhea/colitis**, administer oral corticosteroids.
- For **Grade 3 or 4 diarrhea/colitis**, treat with intravenous steroids followed by high dose oral steroids.
- When symptoms improve to Grade 1 or less, steroid taper should be started and continued over no less than 4 weeks.

- **Type 1 diabetes mellitus (if new onset, including diabetic ketoacidosis [DKA]) or ≥ Grade 3 Hyperglycemia, if associated with ketosis (ketonuria) or metabolic acidosis (DKA)**
  - For **T1DM** or **Grade 3-4** Hyperglycemia
    - Insulin replacement therapy is recommended for Type I diabetes mellitus and for Grade 3-4 hyperglycemia associated with metabolic acidosis or ketonuria.
    - Evaluate patients with serum glucose and a metabolic panel, urine ketones, glycosylated hemoglobin, and C-peptide.
- **Hypophysitis:**
  - For **Grade 2** events, treat with corticosteroids. When symptoms improve to Grade 1 or less, steroid taper should be started and continued over no less than 4 weeks. Replacement of appropriate hormones may be required as the steroid dose is tapered.
  - For **Grade 3-4** events, treat with an initial dose of IV corticosteroids followed by oral corticosteroids. When symptoms improve to Grade 1 or less, steroid taper should be started and continued over no less than 4 weeks. Replacement of appropriate hormones may be required as the steroid dose is tapered.
- **Hyperthyroidism or Hypothyroidism:**

Thyroid disorders can occur at any time during treatment. Monitor patients for changes in thyroid function (at the start of treatment, periodically during treatment, and as indicated based on clinical evaluation) and for clinical signs and symptoms of thyroid disorders.

  - **Grade 2** hyperthyroidism events (and **Grade 2-4** hypothyroidism):
    - In hyperthyroidism, non-selective beta-blockers (e.g. propranolol) are suggested as initial therapy.
    - In hypothyroidism, thyroid hormone replacement therapy, with levothyroxine or liothyroinine, is indicated per standard of care.
  - **Grade 3-4** hyperthyroidism
    - Treat with an initial dose of IV corticosteroid followed by oral corticosteroids. When symptoms improve to Grade 1 or less, steroid taper should be started and continued over no less than 4 weeks. Replacement of appropriate hormones may be required as the steroid dose is tapered.
- **Hepatic:**
  - For **Grade 2** events, monitor liver function tests more frequently until returned to baseline values (consider weekly).
    - Treat with IV or oral corticosteroids
  - For **Grade 3-4** events, treat with intravenous corticosteroids for 24 to 48 hours.
  - When symptoms improve to Grade 1 or less, a steroid taper should be started and continued over no less than 4 weeks.
- **Renal Failure or Nephritis:**
  - For **Grade 2** events, treat with corticosteroids.
  - For **Grade 3-4** events, treat with systemic corticosteroids.
  - When symptoms improve to Grade 1 or less, steroid taper should be started and continued over no less than 4 weeks.

**Table 4. Supportive Measures**

Toxicity	Grade	Supportive Treatment
Pneumonitis 	2	Treat with systemic corticosteroids 
	3-4	Immediately treat with intravenous steroids. Administer additional anti-inflammatory measures, as needed
Diarrhea/Colitis 	2	Administer oral corticosteroids 
	3-4	Treat with intravenous steroids followed by high dose oral steroids.
Type 1 diabetes mellitus (if new onset) or Hyperglycemia 	T1D M or 3-4	Insulin replacement therapy is recommended for Type I diabetes mellitus and for Grade 3-4 hyperglycemia associated with metabolic acidosis or ketonuria.
Hypophysitis	2	Treat with oral corticosteroids 
	3-4	Treat with intravenous steroids followed by high dose oral steroids 
Hyperthyroidism	3	Non-selective beta-blockers (e.g. propranolol) are suggested as initial therapy.
	4	Treat with an initial dose of IV corticosteroid followed by oral corticosteroids
Hypothyroidism	2-4	Thyroid hormone replacement therapy, with levothyroxine or liothyroinine, is indicated per standard of care 
Hepatic Reaction	2	Monitor liver function tests more frequently until returned to baseline values (consider weekly)
	3-4	Treat with intravenous corticosteroids for 24 to 48 hours 
Renal Failure or Nephritis	2	Treat with oral corticosteroids 
	3-4	Treat with intravenous steroids followed by high dose oral steroids 

 
1) Add prophylactic antibiotics for opportunistic infections in the case of prolonged steroid administration.
 
2) When symptoms improve to Grade 1 or less, steroid taper should be started and continued over no less than 4 weeks.
 
3) All subjects who experience diarrhea/colitis should be advised to drink liberal quantities of clear fluids. If sufficient oral fluid intake is not feasible, fluid and electrolytes should be substituted via IV infusion.
 
4) For Grade 2 or higher diarrhea, consider GI consultation and endoscopy to confirm or rule out colitis.
 
5) Evaluate patients with serum glucose and a metabolic panel, urine ketones, glycosylated hemoglobin, and C-peptide.
 
6) Replacement of appropriate hormones may be required as the steroid dose is tapered.
 
		

- **Management of Infusion Reactions:** Signs and symptoms usually develop during or shortly after drug infusion and generally resolve completely within 24 hours of completion of infusion.

The table below shows treatment guidelines for subjects who experience an infusion reaction associated with administration of pembrolizumab (MK-3475).

